## 2. SYNOPSIS

Title of Study:	A Multicenter, Post Market, Prospective Study Evaluating Safety and Efficacy of CONQUEST FN™ for the Treatment of Intracapsular Femoral Neck Fractures
Study Design:	Prospective, single arm, multi-center study of subjects who are to be implanted with the CONQUEST FN™ Femoral Neck Fracture System for treatment of a trauma related femoral neck fracture.
Study Type:	Post-Market Clinical Follow-Up (PMCF)
Study Product:	The CONQUEST FN™ Femoral Neck Fracture System
Study Purpose:	A post-market, prospective study to evaluate the reoperation rate of displaced and nondisplaced femoral neck fractures treated with the CONQUEST FN™ system.
Primary Objective:	The primary objective of this study is to evaluate the reoperation rate for any reason of displaced and non-displaced femoral neck fractures treated with the CONQUEST FN™ Femoral Neck Fracture System at one year post-operation.
Secondary Objective(s):	The secondary objective of this study is to generate safety and performance evidence for the CONQUEST FN™ Femoral Neck Fracture System via the collection of functional outcomes, quality of life, and safety data.
Statistical Rationale:	A total minimum sample size of 90 subjects with a minimum of 45 subjects for displaced and 45 subjects for non-displaced femoral neck fractures. Since the primary and secondary endpoints are the same for all fractures, overall results will be reported as well.
Sample Size:	A minimum of 90 Subjects (minimum of 45 displaced and 45 non-displaced femoral neck fractures)
Number of Study Sites:	Approximately 10 sites
Targeted Global Regions:	United States
Inclusion Criteria:	
 
1. The subject must provide written informed consent (reference section 7.4).
 

### CONFIDENTIAL AND PROPRIETARY

This document contains information that is confidential and proprietary to Smith & Nephew PLC and Smith & Nephew, Inc. and is intended for use only by Smith & Nephew and its manufacturer. It shall not be reproduced or copied in whole or in part, nor shall the contents be disclosed by any means without prior written permission from Smith & Nephew, nor shall anyone make any use of it that is contrary to the expressed or implied wishes of Smith & Nephew.

Study Protocol—Device	
A Multicenter, Post Market, Prospective Study Evaluating Safety and Efficacy of CONQUEST FN™ for the Treatment of Intracapsular Femoral Neck Fractures	Number: 18-3047-02 Version: 2.0, 30Nov2018 Page: Page 4 of 63

2. The subject must be eighteen (18) years of age or older.
  3. The subject must be willing and able to make all required study visits including one (1) year post-operative follow-up.
  4. The subject must be able to follow instructions.
  5. Subject has experienced displaced or non-displaced intracapsular femoral neck fracture and are scheduled for repair using the CONQUEST FN™ Femoral Neck Fracture System.
- Exclusion Criteria:**
1. Contraindications or hypersensitivity to the use of the CONQUEST FN™ Femoral Neck Fracture System or its components (316L stainless steel).
  2. Subject with fracture occurring more than 7 days prior to implantation of the CONQUEST FN™ Femoral Neck System.
  3. Subject has more than one fracture on target hip.
  4. Subject is obese as defined by a Body Mass Index (BMI) > 40 at the time of surgery.
  5. Subject, in the opinion of the Investigator, has an emotional or neurological condition that precludes cooperation and compliance with the rehabilitation regimen.
  6. Therapy with another investigational agent within thirty (30) days of Screening or planned therapy with another investigational agent during the course of the study.
  7. Subject has a physical condition that, in the opinion of the Investigator, would preclude adequate implant support or impede healing (e.g. blood supply impairment, insufficient bone quality or quantity, or an active, local or systemic infection). If this is identified at the time of surgery, the subject will be screen failed.
  8. Subject has undergone previous surgery on the target hip.
  9. Subject has severe bow of the target hip or gross distortion of the femur.

#### **CONFIDENTIAL AND PROPRIETARY**

This document contains information that is confidential and proprietary to Smith & Nephew PLC and Smith & Nephew, Inc. and is intended for use only by Smith & Nephew and its manufacturer. It shall not be reproduced or copied in whole or in part, nor shall the contents be disclosed by any means without prior written permission from Smith & Nephew, nor shall anyone make any use of it that is contrary to the expressed or implied wishes of Smith & Nephew.

Study Protocol—Device	
A Multicenter, Post Market, Prospective Study Evaluating Safety and Efficacy of CONQUEST FN™ for the Treatment of Intracapsular Femoral Neck Fractures	Number: 18-3047-02 Version: 2.0, 30Nov2018 Page: Page 5 of 63

	
10. Subjects who have participated previously in this clinical trial and who have healed or been withdrawn.
 
11. Current systemic therapy with cytotoxic drugs.
 
12. Subjects with a history of poor compliance with medical treatment.
 
13. Subjects with a medical or physical condition that, in the opinion of the Investigator, would preclude safe subject participation in the study.

Study Duration:	Approximately 30 months (18 month recruitment period, 12 month follow-up)
Primary endpoint:	Reoperation rate for any reason of displaced and non-displaced femoral neck fractures treated with the Conquest FN™ at one year post-operation.
Secondary endpoint(s):	
The secondary endpoints of this study include generation of safety, performance, and health economic evidence supporting the use of the CONQUEST FN™ Femoral Neck Fracture System per the endpoints listed below:
 
 
• Intraoperative complications
 
• Radiographic outcomes including quality of fracture reduction
 
• Construct failure past typical femoral neck fracture healing period (past 6 months)
 
• Visual analogue scale (VAS) relating to pain at the fracture site
 
• Quality of Life (EQ-5D-5L)
 
• Time to return to full weight-bearing
 
• Ambulatory status from pre-injury to study completion
 
• Timed Up & Go
 
• Length of hospital stay
 
• Hospital readmissions for any reason
 
• Device- and surgery-related adverse events
 
• Active straight leg raise (ASLR) assessment
 

Safety Data	Adverse Events will be collected and categorized in terms of seriousness and relatedness to the study device or to the surgical procedure. All Serious Adverse Device Effects will be further categorized as Anticipated or Unanticipated. All events, based on these categorizations, will be reported to appropriate regulatory authorities

## STUDY SCHEMATIC

Schedule of events	Pre-Operative Data (Day -7 to Day 0)	Operative/Discharge Data  (Day 1)	6 weeks (Day 42 ± 7 days)	3 months (Day 90 ± 7 days)	6 months (Day 180 ± 14 days)	12 months (Day 365 ± 30 days)
Informed Consent	✓					
Inclusion/Exclusion	✓					
Demographics/Medical History	✓					
Operative Data Collection		✓				
Discharge Data Collection 		✓				
VAS (pain score)	✓		✓	✓	✓	✓
Timed Up & Go			✓	✓	✓	✓
EQ-5D-5L	✓		✓	✓	✓	✓
X-Ray						
• AP	✓	✓	✓	✓	✓	✓
• Lateral						
Active Straight Leg Raise			✓	✓	✓	✓
Adverse Event Assessment		✓	✓	✓	✓	✓
End of Study/Exit						✓

 Discharge data to be collected at time of discharge which will be dependent on subject recovery.

### 3.3 LIST OF ABBREVIATIONS

Abbreviation	Definition
ASLR	Active Straight Leg Raise
ADE	Adverse Device Effect(s)
AE	Adverse Event(s)
AP	Anteroposterior
CRF	Case Report Form(s)
CV	Curriculum Vitae
DevD	Device Deficiency(ies)
FAS	Full Analysis Set Population
FU	Follow-up
GCP	Good Clinical Practice
ICH	International Conference on Harmonisation
IEC	Independent Ethics Committee
IFU	Instructions for Use
IRB	Institutional Review Board
ITT	Intention to Treat population
MedDRA	Medical Dictionary for Regulatory Activities
NA or N/A	Not Applicable
N (or n)	Total Sample Size (or subgroup sample size)
PI	Principal Investigator
PP	Per-protocol Population
S&N	Smith & Nephew Inc.
SADE	Serious Adverse Device Effect(s)
SAE	Serious Adverse Event(s)
SAF	Safety population

#### CONFIDENTIAL AND PROPRIETARY

This document contains information that is confidential and proprietary to Smith & Nephew PLC and Smith & Nephew, Inc. and is intended for use only by Smith & Nephew and its manufacturer. It shall not be reproduced or copied in whole or in part, nor shall the contents be disclosed by any means without prior written permission from Smith & Nephew, nor shall anyone make any use of it that is contrary to the expressed or implied wishes of Smith & Nephew.

Study Protocol—Device	
A Multicenter, Post Market, Prospective Study Evaluating Safety and Efficacy of CONQUEST FN™ for the Treatment of Intracapsular Femoral Neck Fractures	Number: 18-3047-02
	Version: 2.0, 30Nov2018
	Page: Page 11 of 63

Abbreviation	Definition
SAP	Statistical Analysis Plan
TUG	Timed Up and Go
USADE	Unanticipated Serious Adverse Device Effect(s)
VAS	Visual Analog Scale

## 4. INTRODUCTION

### 4.1 BACKGROUND

Femoral neck fractures are major surgical challenges with high complication rates in young (<60 years), young elderly (60-70 years) and elderly adults (>70 years). Relevant literature has reported complication rates ranging from 15–64% and 0-36% for displaced and non-displaced femoral neck fractures, respectively. Complications typically manifest as avascular necrosis, fracture non-union with implant failure and concomitant loss of fracture reduction. In many cases, the onset of these complications necessitates re-operation. The function and anatomy of the proximal femur, including the high regional variability in local load/strain distribution, vascular supply and lack of periosteal fracture response, all contribute in making femoral neck fractures challenging to manage clinically.

Conservative care for high (i.e. traumatic) or low (i.e. fragility) energy femoral neck fractures is rarely a therapeutic option, and so a higher risk surgical intervention is usually the only management choice. Fixation has historically been accomplished using multiple cannulated screws or compression hip screws with or without anti-rotation screws, which act to reduce the fracture and confer compression across the fracture site to allow healing. For high-energy injuries resulting in displaced femoral neck fractures, the quality of fracture reduction is of significant importance, as poorly reduced fractures have been associated with high non-union rates and the need for repeat surgical intervention. While various permutations of these fixation strategies have been utilized clinically, current data do not conclusively support the superiority of a single fixation system or approach for the treatment of intracapsular femoral neck fractures and high complication rates persist.

The CONQUEST FN™ represents the next generation femoral neck fracture system designed to offer better intra-operative reduction control with the assurance of eliminating device failure modes. This system is dedicated to treating both non-displaced and displaced intracapsular fractures of the femoral neck. It is a dynamic locked implant system that provides multiple points

#### CONFIDENTIAL AND PROPRIETARY

This document contains information that is confidential and proprietary to Smith & Nephew PLC and Smith & Nephew, Inc. and is intended for use only by Smith & Nephew and its manufacturer. It shall not be reproduced or copied in whole or in part, nor shall the contents be disclosed by any means without prior written permission from Smith & Nephew, nor shall anyone make any use of it that is contrary to the expressed or implied wishes of Smith & Nephew.

Study Protocol—Device	
A Multicenter, Post Market, Prospective Study Evaluating Safety and Efficacy of CONQUEST FN™ for the Treatment of Intracapsular Femoral Neck Fractures	Number: 18-3047-02
	Version: 2.0, 30Nov2018
	Page: Page 13 of 63

of fixed angle support with continuous compression across the fracture site, ensuring bone-on-bone contact during the fracture union process. The continuous fracture site compression and post-operative reduction maintenance is accomplished with the incorporation of telescoping compression screw technology. The novel system empowers surgeons to address the current surgical challenges and often unfavorable patient outcomes and high re-operation rate associated with the current treatment options for intracapsular femoral neck fractures.

The CONQUEST FN™ Femoral Neck Fracture System obtained 510(k) clearance from FDA on 17Mar2016. To date, it is being used in clinical practice by several institutions in the United States with approximately sixty (60) cases in which the system has been implanted. Clinical studies on the system are needed to provide evidence to assess overall safety and efficacy. A summary of known and potential risks and benefits to humans of the Study Device can be found in the Instructions for Use (IFU).

#### **4.2 STUDY PURPOSE**

A post-market, prospective study to evaluate the reoperation rate of displaced and nondisplaced femoral neck fractures treated with the CONQUEST FN™ system. Safety Considerations

Reference the current Instructions for Use (IFU) for a comprehensive list on known contraindications and safety considerations.

## 5. OBJECTIVE(S)

### 5.1 PRIMARY OBJECTIVE

The primary objective of this study is to evaluate the re-operation rate for any reason of displaced and non-displaced femoral neck fractures treated with the CONQUEST FN™ Femoral Neck Fracture System at one year post-operation.

### 5.2 SECONDARY OBJECTIVE(S)

The secondary objective of this study is to generate safety and performance evidence for the CONQUEST FN™ Femoral Neck Fracture System via the collection of functional outcomes, quality of life, and safety data.

## 6. STUDY DEVICE(S)

### 6.1 IDENTIFICATION

#### 6.1.1 Study Product

##### *Intended Use*

The CONQUEST FN™ Femoral Neck Fracture System is indicated for use in displaced and non-displaced intracapsular femoral neck fractures. The present study aims to evaluate the use of CONQUEST FN™ in adults ( $\geq 18$  years of age) who have suffered a femoral neck fracture due to trauma but are otherwise active individuals.

##### *Device description*

The CONQUEST FN™ is a dynamic locking plate system that includes a proximal femoral locking plate, telescoping compression screws, and reduction maintenance instrumentation. The proximal femoral locking plate is available in three sizes (left and right) (see figure 6.1.1-1), all of which are comprised of 316L Stainless Steel with a neck angle of 124 degrees and anteversion of 14 degrees. The telescoping compression screws are available in two (2) circumference sizes, 7.5mm and 8.5mm, which are also comprised of 316L Stainless Steel with lengths ranging from 75mm-130mm (5mm increments).

##### *Manufacturer*

[figure not shown]
CONQUEST FN™ is manufactured by Smith & Nephew, Inc., [name].

**Figure 6.1.1-1 CONQUEST FN™ Femoral Neck Fracture System (Not Actual Size)**

#### **CONQUEST FN Locking Plates 60mm**

Set No. 7181-1401

Cat. No.	Description	Quantity
7580-7001L	CONQUEST FN Locking Plate 1H Left 60mm	1
7580-7001R	CONQUEST FN Locking Plate 1H Right 60mm	1

#### **CONQUEST FN Locking Plates 85mm**

Set No. 7181-1401

Cat. No.	Description	Quantity
7580-8002L	CONQUEST FN Locking Plate 2H Left 85mm	1
7580-8002R	CONQUEST FN Locking Plate 2H Right 85mm	1

#### **CONQUEST FN™ Locking Plates 127mm**

Set No. 7181-1401

Cat. No.	Description	Quantity
7580-7003L	CONQUEST FN Locking Plate 3H Left 127mm	1
7580-7003R	CONQUEST FN Locking Plate 3H Right 127mm	1

### **6.1.2 IP-Control and Comparator Treatment**

There will be no comparator products used in this study.

### **6.1.3 Ancillary Products**

No ancillary products are to be provided for this study.

## 6.2 PRODUCT USE

Refer to IFU and Surgical Technique educational brochure for full instructions.

Study center personnel with responsibilities for the medical care of subjects and/or the implantation of the study device (CONQUEST FN™) will be trained on the use and surgical techniques of CONQUEST FN™ prior to enrolling subjects in the study.

## 6.3 PACKAGING AND LABELING

Packaging and labelling will be prepared to meet regulatory requirements.

### 6.3.1 Study Device Labeling

Smith & Nephew will not supply the site with study devices due to the various size options available for use. Standard device procurement and management will be used per site processes.

## 6.4 STUDY DEVICE/ ANCILLARY PRODUCTS AND STUDY SUPPLIES ACCOUNTABILITY PROCEDURES

No Study device/Ancillary Products and Study Supplies are supplied for the study and the Sponsor accountability will not be required.

## 6.5 SURGICAL TECHNIQUE

All study-related procedures conducted at the study site must be performed according to the recommended surgical technique described in the labeling and instructions for use (IFU).

Surgeons selected to participate in this study will be required to have completed two (2) surgeries using the CONQUEST FN™ Femoral Neck Fracture System and have written evidence of training and expertise in the study procedure.

## 7. SUBJECT ENROLLMENT AND WITHDRAWAL

### *Subject Population*

A minimum of 90 subjects (18 years of age or older) with a confirmed displaced or non-displaced intracapsular femoral neck fracture who are scheduled for repair using CONQUEST FN™ will be recruited at approximately 10 study sites in the United States. Additional sites may be added, if necessary, to meet recruitment goals. A minimum of 45 displaced and 45 non-displaced fractures are required.

#### 7.1 INCLUSION CRITERIA

Subjects will be considered qualified for enrollment if they meet the following criteria:

1. The subject must provide written informed consent (reference section 7.4).
2. The subject must be eighteen (18) years of age or older.
3. The subject must be willing and able to make all required study visits including one (1) year post-operative follow-up.
4. The subject must be able to follow instructions.
5. Subject has experienced displaced or non-displaced intracapsular femoral neck fracture and is scheduled for repair using the CONQUEST FN™ Femoral Neck Fracture System.

#### 7.2 EXCLUSION CRITERIA

Any one (1) of the following criteria will disqualify a potential subject from participation in the study:

1. Contraindications or hypersensitivity to the use of the CONQUEST FN™ Femoral Neck Fracture System or its components (e.g. stainless steel).
2. Subject with fracture occurring more than 7 days prior to implantation of the CONQUEST FN™ Femoral Neck System.
3. Subject has more than one fracture on target hip.
4. Subject is obese as defined by a Body Mass Index (BMI) > 40 at the time of surgery.

### CONFIDENTIAL AND PROPRIETARY

This document contains information that is confidential and proprietary to Smith & Nephew PLC and Smith & Nephew, Inc. and is intended for use only by Smith & Nephew and its manufacturer. It shall not be reproduced or copied in whole or in part, nor shall the contents be disclosed by any means without prior written permission from Smith & Nephew, nor shall anyone make any use of it that is contrary to the expressed or implied wishes of Smith & Nephew.

Study Protocol—Device	
A Multicenter, Post Market, Prospective Study Evaluating Safety and Efficacy of CONQUEST FN™ for the Treatment of Intracapsular Femoral Neck Fractures	Number: 18-3047-02
	Version: 2.0, 30Nov2018
	Page: Page 19 of 63

- 5. Subject, in the opinion of the Investigator, has an emotional or neurological condition that precludes cooperation and compliance with the rehabilitation regimen.
- 6. Therapy with another investigational agent within thirty (30) days of Screening or planned therapy with another investigational agent during the course of the study.
- 7. Subject has a physical condition that, in the opinion of the Investigator, would preclude adequate implant support or impede healing (e.g. blood supply impairment, insufficient bone quality or quantity, or an active, local or systemic infection). If this is identified at the time of surgery, the subject will be screen failed.
- 8. Subject has undergone previous surgery on the target hip.
- 9. Subject has a severe bow of the target hip or gross distortion of the femur.
- 10. Subjects who have participated previously in this clinical trial and who have healed or been withdrawn.
- 11. Current systemic therapy with cytotoxic drugs.
- 12. Subjects with a history of poor compliance with medical treatment.
- 13. Subjects with a medical or physical condition that, in the opinion of the Investigator, would preclude safe subject participation in the study.

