#### **7.5 ENROLLMENT**

Enrollment in this study shall occur once the subject has successfully completed the informed consent process and successfully completed the Operative Visit (Day 1). A subject number will be assigned at the time of the Screening visit.

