#### 8.4.2 Screening/Preoperative Visit

NOTE: Any subject who signs an informed consent but fails to meet the required entry criteria is considered to be a Screen Failure. Screen Failure subjects will be assigned subject numbers and their demographic information will be captured in the appropriate CRF with the reason for screen failure specified.

1. Obtain written informed consent from the subject as detailed in Section 7.4  

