#### 8.4.3 Baseline/Operation Visit (Day 1)

NOTE: If the Investigator decides a subject should not receive the Study Device for any reason at the time of surgery, the subject will be considered a Screen Failure and the reason for non-enrollment will be clearly documented in the subject's source documents.

1. Query subject regarding any changes in general health and the use of concomitant medications.
2. If any adverse device effects or device deficiencies are observed or reported, they must be recorded as instructed in Section 11, adverse events and device deficiencies.
3. Perform surgery per current CONQUEST FN™ Instructions for Use (IFU).
4. Collect study-specific operative data.
5. Perform radiology imaging collecting both anteroposterior (AP) and lateral images of the target hip to ensure the CONQUEST FN™ is properly implanted.
6. Collect study-specific discharge data.
7. Instruct the subject on proper postoperative care documenting the prescribed rehabilitation plan in the subject's source document.
8. Instruct the subject on follow-up procedures, including returning to the office for Follow-up (FU) Visit 1 in 42 ( $\pm$  7) days.

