## 9.2 ANALYSIS POPULATIONS

- Intention to Treat population (ITT), including all subjects randomized into the study.
- Full analysis set population (FAS), following Intention to Treat principle including all subjects who were randomized into the study and attended at least one post-baseline assessment
- Safety Population (SAF), including all subjects who have received the IP or the control devices.
- Per-Protocol Population (PP), including all subjects in the full analysis set who have no significant protocol deviations and met the inclusion/exclusion criteria.

Statistical analysis will be performed using each of the patient populations as follows. Analysis of the primary, secondary and exploratory efficacy objectives will be performed separately using both the Full Analysis Set and the Per Protocol Population. All safety analyses will utilize the Safety Population.

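### Exclusion 7 does not limit screen failure at surgery to subjects left without the device, which is not reconciled with Sections 8.4.3 and 9.2; applied as worded to an implanted hip, it would take that hip out of the re-operation rate

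*Combined protocol and SAP*

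**What the plan says.** Item 7 of Section 7.2, repeated in the Synopsis, excludes a subject whose physical condition, in the investigator's opinion, "would preclude adequate implant support or impede healing (e.g. blood supply impairment, insufficient bone quality or quantity, or an active, local or systemic infection"). It ends: "If this is identified at the time of surgery, the subject will be screen failed." Whether the device has been, or will be, implanted is not mentioned.

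Section 8.4.3 has its own rule for the operative visit: "If the Investigator decides a subject should not receive the Study Device for any reason at the time of surgery", the subject is a screen failure. That rule depends on the device not being given.

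Four other places decide what happens to a screen failure:

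- Section 7.5 places enrollment after consent and after successful completion of the operative visit. Successful completion is not defined.
- Section 8.4.2 makes anyone who consents but fails the entry criteria a screen failure. For these subjects, "their demographic information will be captured in the appropriate CRF with the reason for screen failure specified". No follow-up is described.
- The replacement policy in Section 7.7.1 replaces subjects lost before enrollment and not those lost afterwards.
- Section 9.2 analyses the efficacy objectives in the FAS and the Per-Protocol set, but defines the "Safety Population (SAF), including all subjects who have received the IP or the control devices".

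**The concern.** The study has one arm and no comparator, so the one-year re-operation proportion in each fracture group is the main result. Its meaning depends on which implanted hips are counted.

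The second limb of exclusion 7, impeded healing, can be met by a hip that the surgeon still fixes with CONQUEST FN. If the sentence is then followed as written, the subject is removed after implantation or during it, on a judgement about prognosis. The conditions listed (blood supply, bone quality, infection) bear on the failures that Section 4.1 describes: "Complications typically manifest as avascular necrosis, fracture non-union with implant failure and concomitant loss of fracture reduction." The same section says these often lead to re-operation. Removal would therefore be selective and would probably lower the reported rate.

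The same subject would belong to the Safety Population by definition, while the protocol specifies no visits at which later safety data would be collected.

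**Working it through.** **1. The passages side by side, for a subject with the finding at surgery**

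| Provision | Device not implanted | Device implanted and left in place |
|---|---|---|
| 7.2 item 7 | screen failure | screen failure, as worded |
| 8.4.3 note | screen failure | not covered |
| 7.5 | not enrolled | not enrolled if screen-failed |
| 8.4.2 data | number, demographics, reason | number, demographics, reason; follow-up not stated |
| 7.7.1 replacement | replaced | replaced, if treated as lost before enrollment |
| 9.2 FAS and Per-Protocol | out | out |
| 9.2 Safety Population | out | in |

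The provisions agree in the first column. In the second, exclusion 7 and the Safety Population pull in different directions, and no section settles how the subject is followed or analysed.

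**2. The plan's own figures**

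Section 10 assumes success of 87% (displaced) and 93% (non-displaced), with precision within 12% and 10%. Taking success as freedom from re-operation, the planning re-operation rates are 13% and 7%. The half-width of the 95% interval is 1.96 × √[p(1 − p)/n]:

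- Displaced, n = 45: 1.96 × √(0.87 × 0.13/45) = 9.8 points; at n = 40, 10.4 points.
- Non-displaced, n = 45: 1.96 × √(0.93 × 0.07/45) = 7.5 points; at n = 40, 7.9 points.

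The stated precision holds. Nothing in this point changes it.

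**3. Possible size of the bias**

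The documents give no frequency for such hips and no re-operation risk, so both inputs here are assumptions. Let p be the rate in the 45 analysed hips, s the share of all implanted hips that are screen-failed, and RR their relative risk. With k = 45s/(1 − s) hips removed, the rate among all implanted hips is

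(45p + k × RR × p)/(45 + k) = p × [1 + s(RR − 1)].

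| s | RR | Displaced, p = 13% | Non-displaced, p = 7% |
|---|---|---|---|
| 3% | 2 | 13.4% | 7.2% |
| 3% | 3 | 13.8% | 7.4% |
| 5% | 2 | 13.7% | 7.4% |
| 5% | 3 | 14.3% | 7.7% |
| 10% | 2 | 14.3% | 7.7% |
| 10% | 3 | 15.6% | 8.4% |

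The understatement is 0.4-2.6 points (displaced) and 0.2-1.4 points (non-displaced).

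**4. A second set of assumptions**

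Suppose k = 1 to 5 hips per group are removed, each with an absolute re-operation risk q of 30-50%. The rate is (45p + kq)/(45 + k).

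- Displaced: (5.85 + 0.3)/46 = 13.4% up to (5.85 + 2.5)/50 = 16.7%.
- Non-displaced: (3.15 + 0.3)/46 = 7.5% up to (3.15 + 2.5)/50 = 11.3%.

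The understatement is then about 0.4-3.7 and 0.5-4.3 points.

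**5. One uncounted re-operation**

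Adding one removed hip that was re-operated gives (5.85 + 1)/46 = 14.9% (displaced, up 1.9 points) or (3.15 + 1)/46 = 9.0% (non-displaced, up 2.0 points).

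**The case against.** A reader might infer that the protocol does remove the highest-risk implanted hips from follow-up and from the primary rate. The documents do not support that as a statement of fact. No passage says that a subject is screen-failed although CONQUEST FN has been implanted and left in place. Section 8.4.3, which governs the operative visit, describes screen failure there as a decision not to give the device, and the first limb of exclusion 7 (inadequate implant support) fits such a decision. If exclusion 7 is only one instance of that rule, no implanted hip is lost.

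Against this, it can be said that on the narrow reading the sentence adds nothing to Section 8.4.3, and that the amendment log shows it was added to Section 7.2 in Version 2.0. That argument is not decisive. Section 8.4.2 already makes anyone who fails the entry criteria a screen failure, so the sentence overlaps an existing rule on either reading and may only clarify timing.

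Three further objections have weight:

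- It would be too strong to say that these subjects have no safety data. Section 8.4.3 requires adverse device effects and deficiencies to be recorded at the operative visit, and follow-up after a screen failure is unstated, not prohibited. The gap is in what follows surgery.
- Exclusion 7 defines the eligible population, so part of the concern is generalisability and not bias. However, Section 5.1 states the objective for fractures treated with the device, and an implanted hip belongs to that group.
- The calculated shifts are smaller than the planned half-widths and rest on assumed inputs. Both statements are true. But the confidence interval describes sampling error only and makes no allowance for selective removal.

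What remains is an unconditional sentence that can apply to an implanted hip, and no passage that resolves the case.

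**Conclusion.** The point holds as a conflict between passages with a probable direction of bias. It does not hold as a demonstrated loss of implanted hips. Exclusion 7 does not restrict screen failure at surgery to subjects without the device, and it is not reconciled with Sections 7.5, 8.4.2, 8.4.3 and 9.2. A site that follows the words for an implanted subject would drop that hip from the primary proportion on a prognostic opinion formed during surgery.

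The size is unknown. The ranges in the working depend entirely on assumed frequencies and risks. That the affected hips are at higher risk is inferred from the listed conditions, and no figure in the documents confirms it. If sites apply the narrow reading, the effect is zero. The matter is worth correcting because the primary rate has no comparator and the correction is inexpensive.

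**What to change.** In Section 7.2 item 7 and in the Synopsis, replace the last sentence with wording such as:

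> A subject in whom this is found during surgery, and who does not receive CONQUEST FN, is a screen failure. A subject who leaves surgery with CONQUEST FN in place is enrolled, followed to 12 months and included in the FAS and the Safety Population. The finding is recorded as an eligibility deviation and affects the Per-Protocol set only.

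This is not enough alone, because other text would then contradict it. The following also need to be aligned:

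- the lead-in to Section 7.2, under which any one criterion disqualifies a subject;
- Section 7.5, so that leaving surgery with the device in place counts as enrollment;
- the screen-failure note in Section 8.4.2, so that it excepts implanted subjects;
- the FAS definition in Section 9.2, which refers to randomized subjects although Section 8.2 says the study is not randomized; it should refer to implanted and enrolled subjects. It also requires attendance at a post-baseline assessment, and the sponsor should state whether that condition still applies to these subjects.

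The report should give the number of screen failures at surgery, by whether the device was implanted.

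The cost is a short amendment in several places, a few more subjects to follow and possibly a slightly less favourable re-operation rate. The surgeon's decision whether to implant is unchanged.
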